1. Utilize the unique patient clinical data that is available with the mymobility application to correlate early post-operative outcomes of various implant groups (e.g. brand, type, manufacturer) to preoperative and postoperative activity profiles, surgical techniques, patient attributes, and other routine outcomes data collected.

2. To provide a real-world data set on the mymobility cohort, including physiologic monitoring data, that enables ongoing exploratory data analysis and retrospective cohort study that will inform future product feature development and research. An example of such analysis that would support surgeons to make patient-specific recommendations is: study subjects could be “binned” according to 5-year age grouping (age 30-34, 35-39, etc.) and BMI (20-24, 25-30, etc.), and regression analysis could be used to correlate watch sensor data with superior outcomes. Statistically valid correlations would enable product features that support a surgeon to more easily identify whether or not a given patient’s activity is following a pattern associated with superior clinical outcome.

VII. Study Design and Endpoints

This is a multi-center, staged cohort study evaluating clinical outcomes, economics, and satisfaction with mymobility in the episode of care for the primary THA, TKA and PKA populations. Up to 10,000 subjects will be participating in the mymobility platform. Approximately 500 subjects will participate as a control group in the RCT cohort described in **Section XI**. Up to 36 sites globally will contribute to this study. Each investigator will be experienced in total knee arthroplasty (TKA), partial knee arthroplasty (PKA) or total hip arthroplasty (THA).

Each Principal Investigator will be responsible for obtaining Institutional Review Board (IRB) or Ethics Committee (EC) approval as required prior to conducting the study. In order to avoid potential selection bias, each Investigator will offer study participation to each eligible subject presenting as a candidate for partial or total knee replacement or total hip arthroplasty using approved, commercially-available devices used on-label according to the manufacturer’s instructions for use. The device selection criteria are discussed in **Section VIII**.

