For sites participating in both the Pilot and RCT cohorts, enrollment in the RCT cohort will begin once enrollment is complete at the site for the pilot cohort. Randomization will occur during the pre-operative visit after subjects have signed the ICF for participation in the study. A standard, stratified 1:1 randomization of total hips, total knees, and partial knees will be used to assign subjects to either the mymobility/Apple Watch study group or the standard of care control group. Stratification will ensure that within hips and knees, each procedure type will have a balanced allocation of control

and study patients.

a. Study Group (N=500)

Once randomization is completed, all subjects who were randomized to the mymobility group (mymobility/Apple Watch platform) will undergo all routine study procedures outlined in **Section XI**. In addition, each subject will:

- i. At the preoperative, 30 day and 90 day visits, subjects will undergo a physical exam.
- ii. At the 30 day and 90 day visits, subjects will undergo a Timed Up and Go (TUG) assessment and Single Leg Stance (SLS) assessment. A description of each assessment is listed below:
 - a. TUG assessment: the subject will be asked to rise from a sitting position, walk 3 meters as quickly as they feel safe and comfortable, turn around and walk back to take a seat in the chair. They will be timed from initiation of standing to a return to the sitting position. The subject will get one practice trial prior to scoring the assessment.
 - b. SLS assessment: Three, one-minute maximum, timed observations will be obtained. The average of the three timed observations will be calculated at the time of data analysis.

b. Control Group (N=500)

Subjects randomized to the control group will undergo traditional, standard of care procedures at their institution without the use of the mymobility platform

- i. Control subjects will receive the standard of care (SOC) at the institution, including postoperative PT, and go through normal preoperative standard of care including joint camp classes, preoperative medical clearance, and traditional preoperative education.
- ii. Control subjects will not be provided with the Apple Watch or mymobility App.
- iii. Control subjects will go through each institution's standard of care (SOC) perioperative management pathway.

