During the course of the study, the Sponsor, or designee, will conduct periodic central or onsite monitoring and maintain contact with the study staff to monitor compliance and evidence of adverse events, in accordance with the Sponsor's policies and procedures. The Sponsor will address any identified non-compliance with the executed CTA, study protocol, and applicable regulatory requirements.

If onsite monitoring visit(s) are deemed appropriate by the Sponsor, the Investigator will permit representatives of the Sponsor's monitoring team to have direct access to inspect all source data/documents, study documents/binders, corresponding sections of study subject medical/hospital records, and any other documents relevant to the study. All Sponsor onsite visits (including site initiation) will be documented using the Site Monitoring Visit Log.

XV. Risk Analysis

The control group in this study receives the institutional standard of care, which may vary from no post-operative rehabilitation to inpatient rehabilitation. The study group is managed with one specific postoperative protocol: the utilization of computer-based perioperative care. Computer-based rehabilitation protocols have been previously described and are the standard of care at many institutions. The specific computer-based platform utilized in this study includes an Apple Watch and the mymobility application.

While this combination of new technologies provides the patient and surgeon with a more structured, efficient and informed perioperative experience, there is no specific intervention or postoperative recommendation involved in this study that is considered to be outside of the current standard of care. The study group is receiving one of the current standards of perioperative care, being delivered through a novel combination of technologies.

There are several categories of risk that may be relevant in this study.

A. Risks

1. Risk of Privacy Breach

The Sponsor has put in place physical, electronic, and administrative safeguards to help protect the privacy of health information. However, as is the case with all applications, the Sponsor unfortunately cannot guarantee security for data collected, leading to private health information becoming available to others without their

permission.

2. Intraoperative Risk

The study does not involve any alteration to the surgical procedure being performed. Therefore, there is no risk of any intraoperative complication due to this study.

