Subjects using the mymobility application will be evaluated for pain, function, quality of life, and early post-operative outcomes. Data collected in this study will be summarized descriptively and descriptive summaries will be the basis of any study reports issued. These summaries may be used for interim study reports and may also be used to support regulatory submissions, presentations, and/or publications. Additional surgical technique and instrumentation data may be collected and evaluated.

A. General Statistical Methods

Statistical methodology will consist of summarizing collected data descriptively. Categorical data (e.g., gender or race) will be summarized using counts and percentages, and 95% Confidence Interval (CI), over the time periods of interest. Continuous data, such as age, will be summarized by using means, medians, standard deviation, minimum, maximum, and 95% CI over the time periods of interest. Routine summaries of complication data is represented by frequencies and percentages. Subgroup analysis on a variety of data will also be performed. Exploratory data analyses using statistical models to discover relationships between demographics, subject adherence, HealthKit data and outcomes will also be performed.

B. General Assumptions

The primary endpoint will be subjected to a power analysis, allowing for an estimation of the number of RCT subjects needed to demonstrate clinically significant differences between outcome measures. Below is the initial analysis on the primary endpoint.

1. Readmission Rate

A 2015 journal article in PLOS ONE used meta-analyses and the University of Wisconsin demonstrated the overall 30-day readmission rate to be 5.4%.³¹ The 5.4% readmission rate is similar to the readmission rates reported in a 2016 JOA article on readmission rates for hips (% across all orthopedics 5.8%) and a 2017 JBJS article on readmission rates for knees (5.8%).

Based on an assumed readmission rate of 5.4% in both the control and study group and a non-inferiority margin of 4.5%, a total sample size of 794 patients will provide 80% power while controlling the alpha-error at 0.05.

C. Sample Size

1. RCT cohort

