The RCT cohort will include 1,000 subjects. This is based on the sample size of 794 required to show non-inferiority on the readmission rate endpoint. Accounting conservatively for 20% Loss-to-follow-up, 1,000 subjects will ensure the study is adequately powered. This study is powered appropriately to show non-inferiority between the mymobility group and control group.

- i. This study is designed to show that the mymobility group is non-inferior to the control group using one primary study endpoint. This will be shown using a closed testing method in which the primary endpoint of readmission rate is compared using $\alpha=0.05$. Study success requires that the study group successfully demonstrates non-inferiority on this end point using the statistical methods described.

2. Apple Watch/mymobility Correlative Analytics

Although there is no well-defined method to calculate the power of a predictive model before it has been developed, the low rate of certain outcomes such as manipulation under anesthesia, readmission, embolism, etc. will increase the number of subjects needed to create a reliably predictive tool that could be used to correlate events and data in order to make claims in clinical decision making. Generally, very large numbers are required to demonstrate predictive power for a predictive statistical model. A goal of 10,000 subjects has been set, with interim analyses at 2,500, 5,000 and 7,500 subjects to determine continued need for subject enrollment. Assuming a complication rate of ~3% and a discharge rate of ~5% to postoperative rehab facility in the study population of 10,000 subjects in the Correlative Analytics Cohort, this implies that 300 subjects will have some type of complication and 500 subjects will be discharged to a rehab facility. Given the fact that our goals are to identify high positive predictive value and area under the curve (AUC) upper and lower threshold values of Apple Watch measured and transmitted biometric data (steps, stand hours, active calories, exercise minutes, heart rate - resting, walking, variability, flights climbed), using multivariate regression to correlate with post-op complications, and risks of discharge to rehab facility, we would conclude that a Predictive Signatures Study group of at least 10,000 subjects will be required.

Examples of other studies in the total joint literature that have used multivariate regression models to provide clinically useful cutoff values are provided below:

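### Site enters neither the stated RCT stratification nor any RCT comparison, so secondary and resource-use results may be less precise than the data allow

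*Combined protocol and SAP*

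**What the plan says.** Section XI.B.2 of the combined protocol and SAP describes the allocation: "A standard, stratified 1:1 randomization of total hips, total knees, and partial knees will be used to assign subjects". The stated aim is balance by procedure: "Stratification will ensure that within hips and knees, each procedure type will have a balanced allocation of control" and study patients. Site is not mentioned as a stratum. No block size is given, and nothing says whether lists are central or per site.

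On the comparator, the control-group part of Section XI.B.2 says: "Control subjects will go through each institution's standard of care (SOC) perioperative management pathway". Section XV (Risk Analysis) adds: "The control group in this study receives the institutional standard of care, which may vary from no post-operative rehabilitation to inpatient rehabilitation". On the number of centres, Section VII says: "Up to 36 sites globally will contribute to this study". That is the cap for all three cohorts together; the number of RCT sites is not stated. On size, Section XVI.C says: "The RCT cohort will include 1,000 subjects".

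On analysis, Section XVI.A says: "Statistical methodology will consist of summarizing collected data descriptively", and "Subgroup analysis on a variety of data will also be performed". Section XVI.C adds one non-inferiority comparison of readmission at alpha 0.05. No covariate, site term or stratified method is named for any RCT endpoint. Section VII lists the RCT secondary endpoints: HOOS, JR., KOOS, JR., EQ-5D-5L, manipulation, TUG, SLS, satisfaction and resource use, the last including PT visits and discharge disposition.

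**The concern.** In this trial the institution largely defines the comparator. It can also influence the study arm: Section XI.A lets surgeons prescribe PT to app users at any time, discharge habits are local, and TUG and SLS are timed by site staff at visits. Site is therefore a plausible strong predictor of several secondary and resource outcomes.

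If allocation is not balanced within site and the analysis ignores site, between-site variation enters the error of the arm difference. Intervals are then wider than the collected data require. In a single realised trial, one arm may also hold more subjects from PT-heavy or facility-discharge sites. The resource comparison carries the economic objective, so this is where the loss would matter most.

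**Working it through.** **The plan's own figure.** Inputs from Section XVI.B: 5.4% readmission in both arms, margin 4.5%, 80% power, alpha 0.05. Per arm, n = 2 × 0.054 × 0.946 × (1.960 + 0.842)² / 0.045² = 396.002, rounded up to 397, so 794 in total. This matches the plan, with alpha 0.05 acting as two-sided. (One-sided 0.05 would give 624.) Dividing 794 by 0.8 gives 993, consistent with 1,000.

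**Effect on readmission.** If site adjustment removes a share ICC of the variance, 794 becomes 786, 778 or 754 at ICC 0.01, 0.02 or 0.05. Power at 397 per arm moves from 80.1% to 80.5%, 80.9% or 82.1%. The effect is small.

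**Imbalance within a site.** Assume 1,000 subjects, equal-sized sites and allocation not restricted by site. The chance of a split of about 64:36 or worse is twice the lower binomial tail:

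| RCT sites | Subjects per site | Split | Probability |
|---|---|---|---|
| 36 | 28 | 18:10 | 18% |
| 20 | 50 | 32:18 | 6.5% |
| 10 | 100 | 64:36 | 0.7% |

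**Precision when site shifts both arms alike.** Take total variance 1, ICC = share between sites, K sites, N = 1,000. The unadjusted difference has variance 4/N. With a site intercept it is about 4(1 − ICC)/(N − K). The ratio is (1 − ICC) × 1000/(1000 − K).
- ICC 0.1: 0.9 × 1000/964 = 0.934 (K = 36) and 0.9 × 1000/990 = 0.909 (K = 10), a cut of 7-9%.
- ICC 0.3: 0.726 and 0.707, a cut of 27-29%. The inverse, 1/0.707, is about 1.4-fold in effective sample size.

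Allowing for simulation results slightly below the formula, the ranges are about 6-9% and 26-29%. Simulation at ICC 0.2 with 36 sites gave an empirical standard error of 0.062 unadjusted and 0.057 adjusted, with mean error within 0.004 of zero, so no bias.

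**Precision when site acts only in controls.** Here ICC is the between-site share of variance among controls. Control-only site effects add ICC/N to the unadjusted variance, not 4 × ICC/N. The unadjusted variance is then [4(1 − ICC) + ICC]/N, against 4(1 − ICC)/(N − K) adjusted.
- ICC 0.3: 3.1/1000 = 0.00310 against 2.8/964 = 0.00290 (K = 36) or 2.8/990 = 0.00283 (K = 10), a cut of 6-9%.
- ICC 0.1: 3.7/1000 = 0.00370 against 3.6/964 = 0.00373 (K = 36) or 3.6/990 = 0.00364 (K = 10), about −1% to +2%.

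These figures treat the enrolled sites as fixed. If sites are regarded as a sample, ICC/K is added to both variances. At ICC 0.3 and K = 36 that is 0.0083, and the cut shrinks to 0.0002/0.0114, about 2%. This explains why simulations of the control-only case range from nil to about 10%, depending on the target.

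**The case against.** **Where site acts.** The large gains need a site effect common to both arms. The most obvious mechanism here, institution-specific control care, acts mainly in controls, and a common site intercept recovers little of that. This stands: 1.4-fold is an upper bound, not an expectation. Discharge habits, assessors and surgeon-prescribed PT can act in both arms, so the truth probably lies between the two cases.

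**Number of sites.** The 36-site cap covers the whole study. A reader might take 18% as the chance of a poor split in the RCT, but the documents do not support that, because the number of RCT sites is not stated.

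**Silence.** The protocol does not exclude per-site lists. This also stands, but it does not remove the point. With site-stratified allocation and no site term, the reported standard error stays too large: 0.062-0.063 against a true 0.056-0.057 at ICC 0.2. The missing site term is also part of a wider gap, since no model is named for any RCT secondary comparison.

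**Consequence.** Study success rests on readmission alone, which barely moves. Conceded.

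**Control heterogeneity.** The widest range of control care appears only in Section XV, whereas Section XI.B.2 describes control care as including postoperative PT. The two passages must be reconciled, and the plausible ICC depends on which holds.

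**Conclusion.** The point holds as a modest, avoidable loss of precision on RCT secondary and resource endpoints. A reader might infer that omitting site biases the comparison or undermines the non-inferiority conclusion. Neither follows: randomisation keeps the difference unbiased, and the readmission sample size changes by at most 40 of 794 at ICC 0.05.

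The gain from adjustment runs from about nil (site acting only in controls, or ICC near zero) to a variance cut of 26-29% (ICC 0.3, site acting in both arms). All ICCs are assumptions, since the documents give none. High values are most plausible for PT use and discharge disposition, and less certain for TUG and SLS. Fewer RCT sites reduce the within-site imbalance but not the shared-effect gain, which is slightly larger at 10 sites than at 36.

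**What to change.** Before results are seen, prespecify that RCT secondary and resource endpoints are compared with adjustment for procedure and site:
- a site intercept for continuous and count outcomes (PROMs, EQ-5D-5L, TUG, SLS, PT visits);
- a stratified Mantel-Haenszel risk difference for binary outcomes (manipulation, discharge disposition), with small sites pooled by a rule fixed in advance.

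State whether allocation lists are central or per site, and how many sites take part in the RCT.

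If RCT randomisation is still open, site may be added through small blocks or minimisation. Full crossing of 36 sites with 3 procedures gives 108 cells of about 9 subjects (1,000/108), so the scheme must protect the procedure balance already promised. This step may be moot: Version 1.0 is dated May 2018, recruitment was expected to take about 24 months, and Version 4.0 is dated February 2022. The analysis change works either way.

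The cost is SAP wording; no new subjects are needed, and the enrolling site should already be on record for each subject. Small sites must be pooled, and some degrees of freedom are lost. If the ICC is near zero, or site acts only in controls with a low ICC, the price is a slight loss of precision: about 1% of variance at ICC 0.1 with 36 sites.

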The randomized controlled arm of this study aims to demonstrate non-inferiority of the mymobility smartphone (mobile) application (App) with Apple Watch platform in a TJA episode of care, by comparing subjects who receive standard of care (SOC), formal outpatient PT to a study group of subjects who complete remotely guided education and exercise via a mobile application, along with a wearable device. The correlative signature arm will compile key mymobility data, which includes data collected from an Apple Watch, from across the episode of care in TJA to a larger dataset, which will be analyzed to better understand and predict rare events and complications within this population. The purposes of the study are to evaluate the following measures and, as applicable, compare them to the comparator group results:

1. Determine if physical measurements and PROMs are similar between groups
2. Determine if subject satisfaction is higher in the study group
3. Determine the economic benefits to practices, patients and payers
4. Determine if complication outcomes are similar in the study group
5. Determine if the combination of data collected through an episode of care management application on a mobile platform combined with objective physical measurements can be utilized to predict the probability of post-operative complications, discharge disposition, ROM, and other PROM scores. This data set will also be used for future product feature development such as risk stratification, correlative signature modeling, and algorithm development.

VI. Study Objectives

Primary Objectives: The study objectives are to evaluate clinical outcomes, economics, and satisfaction with mymobility and the Apple Watch while developing a correlative heuristic considering multiple endpoints within the THA, TKA and PKA populations. To accomplish the objectives of this multifaceted protocol, the study has been broken into three cohorts with varying objectives. All mymobility study subjects will ultimately be part of the Correlative Analytics cohort. Additional objectives for each cohort are listed below.

A. Pilot & Time Cohort (Cohort I)

Primary Objectives

1. Determine study and product onboarding requirements (time and staff)
2. Determine time required for instrumentation of mymobility App and Apple Watch
3. Determine study execution requirements (time and staff)
4. Verify enrollment assumptions and customized survey content

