Study records in the possession of the Investigator must be retained by the Investigator or Designee for a minimum of 2 years from the Investigator's study termination date, or per applicable local law, regulatory and/or IRB or EC requirements (whichever time period is greater). Measures shall be taken to prevent accidental or premature destruction of study records.

D. Management of Incurrent Events

1. Failure to Obtain Informed Consent and Authorization

Study data will not be collected until the Informed Consent has been signed and dated by the candidate. If a candidate does not wish to participate (does not sign and date the Informed Consent), data for that candidate will not be collected for this

study.

2. Medical Events / Adverse Events

See **Section C Safety Management** – Medical Events/Adverse Events Section of this protocol for additional information regarding adverse event classifications.

All new medical issues or problems reported by patients or found during chart review will be noted on the **Medical Event Log**, which will contain steps to determine whether the event should be considered a reportable adverse event.

Medical events include:

- New medical problems
- New resource utilization such as non-routine visits to a physician, hospital, emergency department, or urgent care center. Routine surgery follow-up visits, vaccinations, and wellness/standard of care visits should not be considered Medical Events.

All medical events determined to be reportable adverse events are required to be reported on the **Adverse Event Form**. The completed **Adverse Event Form** must be submitted to the Sponsor in a timely manner. The Investigator or Designee will also promptly provide the Sponsor with any additional requested information required for the Sponsor to comply with regulatory requirements (including requests for medical records). If applicable per their reporting requirements, the Investigator or Designee will also report applicable adverse event(s) to their IRB/EC.

Adverse events include:

[figure not shown]
- Medical event that is one of the common post-TJR complications
- Medical event that has a relationship to the mymobility app, Apple Watch, procedure, or implant.
- Study joints that receive a treatment of manipulation under anesthesia

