A medical event which is considered to be a normal post-operative symptomology or observation following any joint replacement surgery (e.g. joint pain, swelling, decreased range of motion, incisional pain) should not be classified as an adverse event unless it is considered to be more severe, of longer duration, is otherwise more pronounced than is typical, or is serious. Refer to **Section XIII** for the definition of a Serious Adverse Event. Events occurring after the index joint arthroplasty procedure discharge which are determined by the investigator to not be related to the joint arthroplasty procedure, device, use of the mymobility application or Apple Watch, should not be classified as adverse events, regardless of severity or seriousness.

Medical and adverse event collection will begin only after the patient has study surgery.

Specific instructions regarding Medical Events and Adverse Events:

- Readmission is defined as admittance to a hospital following discharge after the index joint surgery. This includes readmissions for observation as well as same day readmission/discharge. Prolonged hospitalization after the index joint surgery is not considered a readmission.
- If multiple medical events are all associated with the same medical issue, then it may be appropriate that only one adverse event is completed, rather than an adverse event for every medical event.
- Knee codes 30 to 60 are to be used for study joint knee events
- Hip codes 70 to 97 are to be used for study joint hip events
- Codes 01 to 29 are general or non-study joint events

*Normal: anticipated/expected in occurrence, severity, and seriousness. If the event does not meet all three criteria, this should be answered "No."

Reporting and Documentation of Adverse Events and Adverse Device Effects

Adverse Events and Adverse Device Effects will be documented on the Adverse Event Report form over the whole time of the investigation including information on the date of onset, treatment and resolution, as well as assessment of both the seriousness and the relationship to the study device. Further, the outcome of complications will be documented and any changes in outcome are to be updated during the course of the study. In case of early termination of the study, further follow-up of the patient shall proceed according to the hospital's standard procedure.

Reporting and Documentation of Serious Adverse Events, Serious Adverse Device Effects, and Device Deficiencies

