Study subject participation is expected to end upon completion of the subject's last follow-up visit (365 days) unless the subject voluntarily withdraws from the study, is withdrawn from the study by the Investigator, is lost to follow-up, undergoes revision to remove the implanted device, or expires. Reason(s) for study completion must be documented on the **Study Completion Form**.

Some patients might not respond to 1 year surveys and can be considered Lost to Follow-up. Surveys completed beyond 18 months postop should not be collected or entered into the EDC.

If the Sponsor decides to terminate the study early, the Sponsor will inform the Investigators of the reason for early study termination. It is the responsibility of the Investigators to inform their IRB/EC as applicable according to local and national laws/regulations.

9. Modification of the Protocol

All amendments to this protocol shall be agreed to by the Sponsor and the Investigator(s) and be recorded with a justification for the amendment prior to

implementation. Approval of the applicable IRB/EC must be obtained prior to implementation, if required according to the local and/or national laws/regulations.

XIII. Safety Management

Adverse events are required to be reported on the Adverse Event Report case report form. The completed Adverse Event Report case report form must be submitted to the Sponsor in a timely manner. The Investigator or Designee will also promptly provide the Sponsor with any additional requested information required for the Sponsor to comply with regulatory requirements. If applicable per their reporting requirements, the Investigator or Designee will also report applicable adverse event(s) to their IRB or EC.

A. Medical Events/Adverse Events Definitions and Classifications

An adverse event is synonymous with complication or medical event. Adverse events will be classified by type, severity, and outcome and may be collected systematically or non-systematically.

The following definitions are from ISO 14155:2020⁽¹⁾.

Classification of the Event

Adverse Event (AE):

An adverse event is any untoward medical occurrence, unintended disease or injury, or untoward clinical signs (including abnormal laboratory findings) in subjects, users or other persons, whether or not related to the investigational medical device and whether anticipated or unanticipated.

Note 1: This definition includes events related to the investigational medical device or the comparator.

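### The adverse-event relationship list names the app and watch but not physical therapy or other rehabilitation, so rehabilitation injuries are counted by type of rehabilitation and the between-arm harm summary tilts against the app arm

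*Combined protocol and SAP*

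**What the plan says.** Section XII.D.2 (Medical Events / Adverse Events) shows three routes from a medical event to an adverse event:

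- a complication route: "Medical event that is one of the common post-TJR complications";
- a relationship route: "Medical event that has a relationship to the mymobility app, Apple Watch, procedure, or implant";
- manipulation under anesthesia of the study joint.

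The same section then closes the list with a rule for the period after discharge. Events that in the site's judgement prove "to not be related to the joint arthroplasty procedure, device, use of the mymobility application or Apple Watch, should not be classified as adverse events". Serious events get no exception: the rule applies "regardless of severity or seriousness".

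Section XIII.A adopts a wider definition. It covers untoward events whether or not they are related to the device, and its first note adds: "This definition includes events related to the investigational medical device or the comparator".

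On treatment, section XI.B.2.b says: "Control subjects will receive the standard of care (SOC) at the institution, including postoperative PT". It also says that control subjects get neither the app nor the watch. In the app arm, section XI.A.5 discourages formal outpatient PT but lets the surgeon prescribe it at any time.

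On purpose, section V lists: "Determine if complication outcomes are similar in the study group". Section XVI.A says that complications will be summarised as frequencies and percentages.

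**The concern.** The randomized contrast is app-guided home exercise against standard care with in-person PT. Harm arising during rehabilitation is the safety outcome closest to that contrast. Of the four relationship targets, two (app and watch) can apply only in the study arm. The matching control treatment is not a target at all. Two identical injuries, each correctly attributed to the exercise session in which it happened, can be classified differently because one session was run by an app and the other by a therapist.

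At stake is the by-arm summary of adverse events. An excess in the app arm could come from the classification rule, and harm from the comparator could go unrecorded on the Adverse Event Form. More accurate attribution by sites would not remove the difference, because the rule itself creates it.

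**Working it through.** **1. The plan's own figures.** The plan states no adverse-event rate for either RCT arm, so there is none to reproduce. The only RCT size figure is 794, for 30-day readmission (section XVI.B: 5.4% in both arms, margin 4.5 points, 80% power):

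n per arm = 2 × 0.054 × 0.946 × (1.960 + 0.842)² / 0.045² ≈ 396.1, rounded up to 397, so 794 in total.

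This matches at one-sided 0.025. One-sided 0.05 would give 624; the plan does not state sidedness. Adverse events do not enter this calculation. With 1,000 enrolled and 20% lost (section XVI.C), 800 remain, or 400 per arm. That is the denominator used below.

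**2. One injury traced through the rule.** Take a soft-tissue injury after discharge that is not a common post-arthroplasty complication and does not lead to manipulation.

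| Attributed to | Arm in which it can occur | Target named in XII.D.2? | Adverse event? |
|---|---|---|---|
| App-guided exercise only | Study | Yes | Yes |
| In-person PT only | Mainly control, some study | No | No, even if serious |
| Procedure or implant | Both | Yes | Yes |

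Under section XIII.A all three rows would be adverse events: relatedness is not required, and comparator-related events are expressly included. The two sections cannot both be followed for the middle row. Section XIII.A also treats adverse event, complication and medical event as synonyms, whereas XII.D.2 separates medical events from adverse events. It is therefore unclear which count would feed a by-arm complication summary.

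**3. Illustration of size.** Inputs:

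- n = 400 per arm (step 1).
- B = 3%, the complication rate that section XVI.C assumes for the correlative cohort. It is borrowed here for both RCT arms.
- r = true rehabilitation-injury rate, equal in both arms. The documents give none; 0.5% to 2% is assumed.
- q = share of in-person PT injuries called procedure- or implant-related. Not given, so the full range 0 to 1 is shown.

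Assume first that all rehabilitation injuries in the app arm arise in app-guided exercise, and all those in control arise in in-person PT. Then:

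- counted, app arm = n(B + r)
- counted, control = n(B + qr)
- share of control events uncounted = r(1 − q)/(B + r)

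For r = 1%: app = 400 × 0.04 = 16. Control = 400 × 0.03 = 12 at q = 0, 400 × 0.035 = 14 at q = 0.5, and 16 at q = 1.

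| r | q = 0 (app v control; uncounted) | q = 0.5 | q = 1 |
|---|---|---|---|
| 0.5% | 14 v 12; 14% | 14 v 13; 7% | 14 v 14; 0% |
| 1% | 16 v 12; 25% | 16 v 14; 12.5% | 16 v 16; 0% |
| 2% | 20 v 12; 40% | 20 v 16; 20% | 20 v 20; 0% |

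**4. PT in the app arm.** If a share s of app-arm rehabilitation injuries happen in in-person PT, they are unnamed too. With the same q for those injuries, the gap becomes n × r × (1 − q) × (1 − s). Section V mentions that up to 20% of patients cross over to formal PT. Using s = 20% purely as an illustration, r = 1% and q = 0 give 400 × 0.01 × 0.8 = 3.2 events instead of 4. The gap shrinks and keeps its direction.

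**The case against.** The strongest reply is that the text leaves several ways in. Both sentences name the procedure, the investigator makes the judgement, and the sponsor makes the final classification. A fall or strain of the operated limb during post-operative PT can reasonably be called procedure-related. It also counts in either arm if it is a common complication or leads to manipulation. This stands. A reader might infer that control injuries are barred outright, or counted in one arm only. The documents do not support that; only the remainder with no other route is lost.

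Second, 16 v 12 is the worst case on an assumed rate. Even there the difference is 1.0 point, with an approximate 95% interval of −1.5 to +3.5 points (SE = √(0.04 × 0.96/400 + 0.03 × 0.97/400) = 1.3 points). This stands, so the table is a range and not an estimate.

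Third, PT injuries in app-arm subjects are equally unnamed. This stands: the asymmetry is by type of rehabilitation and only partly by arm.

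Fourth, a reader might infer that the trial's main conclusion is affected, or that similarity of complications can no longer be assessed. Neither follows. Readmission is defined without attribution, manipulation has its own route in both arms, and adverse-event rate is not a listed RCT endpoint. No formal test of complications is stated. The Medical Event Log and chart review collect problems in both arms. The log does not cure the defect by itself, because only events that pass the rule go on to the Adverse Event Form, where seriousness, relationship and outcome are recorded.

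Fifth, the event flowchart and the forms are not in the text available, and may handle PT. That cannot be checked. They would still have to agree with the two sentences.

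Last, removing the relatedness requirement altogether would remove this asymmetry as well. That is true, but it is a larger change. If the requirement is kept, rehabilitation still has to be named.

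**Conclusion.** The point holds in a limited form. Sections XII.D.2 and XIII.A conflict over events related to the comparator and must be reconciled. As written, XII.D.2 classifies rehabilitation-attributed injuries by type of rehabilitation. Because in-person PT is expected mainly in the control arm, the descriptive by-arm summary of adverse events and complications is tilted against the app arm and under-records comparator harm.

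The direction rests on PT being more common in control and on some PT injuries having no other qualifying route. The size cannot be computed from the documents. In the illustration at r = 1% the excess is between 0 and 4 counted events per 400, depending on how many PT injuries are called procedure-related. The sample size, the readmission endpoint, the manipulation rate and the Medical Event Log are untouched.

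**What to change.** - In section XII.D.2, add *or any post-operative rehabilitation or physical therapy (either arm)* to the relationship bullet, and make the same addition to the post-discharge exclusion sentence. State how both sentences fit the definition in section XIII.A.
- Carry the addition into the Adverse Event Form and the event flowchart wherever they list relationships.
- Report rehabilitation-related events as one category for both arms, covering app-guided and in-person rehabilitation together.
- For subjects already enrolled, add a by-arm tabulation of Medical Event Log entries that uses no attribution, as a sensitivity analysis. Retrospective re-attribution with the arm evident could itself be biased.

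The cost is a phrase in two sentences, matching edits to the form and flowchart, a few more events to report in both arms, and a little more analysis work. No visits are added and the sample size does not change.
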